3.3 Inclusion of Women and Minorities

Both men and women of all races and ethnic groups are eligible for this trial.

4. REGISTRATION PROCEDURES

4.1 General Guidelines for DF/HCC Institutions

Institutions will register eligible participants in the Clinical Trials Management System (CTMS) OnCore. Registrations must occur prior to the initiation of protocol therapy. Any participant not registered to the protocol before protocol therapy begins will be considered ineligible and registration will be denied.

An investigator will confirm eligibility criteria and a member of the study team will complete the protocol-specific eligibility checklist.

Following registration, participants may begin protocol therapy. Issues that would cause treatment delays should be discussed with the Overall Principal Investigator (PI). If a participant does not receive protocol therapy following registration, the participant's registration on the study must be canceled. Registration cancellations must be made in OnCore as soon as possible.

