4.3 General Guidelines for Other Investigative Sites

Eligible participants will be entered on study centrally at the DF/HCC by the Project Manager. All sites should call the Project Manager at [contact] to verify study slot availabilities.

Following registration, participants should begin protocol therapy within 5 days. Issues that would cause treatment delays should be discussed with the Overall PI. If a participant does not receive protocol therapy following registration, the participant's registration on the study must be canceled. The Project Manager should be notified of cancellations as soon as possible.

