11.2.2 Progression-Free Survival

Overall Survival: Overall Survival (OS) is defined as the time from randomization (or registration) to death due to any cause, or censored at date last known alive.

Progression-Free Survival: Progression-Free Survival (PFS) is defined as the time from randomization (or registration) to the earlier of progression or death due to any cause. Participants alive without disease progression are censored at date of last disease evaluation.

For patients with progression of disease on imaging, it is strongly recommended that a confirmatory biopsy be obtained whenever possible.

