13.7 Reporting and Exclusions

The primary analyses will be on an intent-to-treat basis, considering all patients who are enrolled on study. Secondary analyses and toxicity analyses will be performed on the subset of eligible patients who received at least 1 dose of study drug.

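### Undosed patients' registrations are cancelled and 13.5 requires re-evaluation, so the intent-to-treat set of 13.7 is in practice treated-only or narrower, while PFS and OS still start at registration

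*Combined protocol and SAP*

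**What the plan says.** All references are to the combined protocol and SAP.

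- **Section 4.1 (DF/HCC sites):** for a participant who is registered but gets no protocol therapy, the "registration on the study must be canceled. Registration cancellations must be made in OnCore as soon as possible". Section 4.3 repeats the cancellation rule for other sites and adds: "The Project Manager should be notified of cancellations as soon as possible".
- **Section 4.3 on entry and timing:** "Eligible participants will be entered on study centrally at the DF/HCC by the Project Manager". On the start of therapy: "Following registration, participants should begin protocol therapy within 5 days". Section 4.1 sets no such interval for DF/HCC sites. Both sections refer treatment delays to the Overall PI.
- **Section 13.7:** "The primary analyses will be on an intent-to-treat basis, considering all patients who are enrolled on study". Secondary and toxicity analyses, by contrast, are "performed on the subset of eligible patients who received at least 1 dose of study drug".
- **Section 13.5:** primary and secondary analyses alike are confined to patients with measurable baseline disease who had one cycle or more and a later disease assessment.
- **Section 11.2.2:** PFS is "defined as the time from randomization (or registration) to the earlier of progression or death due to any cause", and OS has the same origin. Section 1.1 describes the study as non-randomized, so the origin is registration.
- **Section 5.6:** survival follow-up begins once protocol therapy is completed or discontinued. Nothing provides for follow-up of a patient who never started.

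**The concern.** Section 13.7 sets all enrolled patients against a subset with at least one dose, so its primary set is evidently meant to be the wider one. The cancellation rule removes the difference: a patient who is registered but never dosed loses the registration by which that patient came on study. Section 13.5 then excludes such patients directly, along with dosed patients who have no later assessment.

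This matters because the exclusion need not be neutral. Section 2.1 describes outcomes as dismal in primary refractory or post-transplant relapsed DLBCL, so some undosed patients may be those who died or deteriorated while waiting. An undosed patient cannot be a responder to the drug. Dropping such patients can therefore raise the response rate or leave it unchanged, but never lower it.

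For PFS and OS the clock starts at registration although membership of the set requires survival to the first dose. The time between the two is immortal time for every analysed patient, and its length may differ by type of site.

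**Working it through.** **1. Who ends up in the primary set.**

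| Patient | 13.7 as worded | After 4.1/4.3 | Under 13.5 |
|---|---|---|---|
| Registered, never dosed | In, if enrolled means registered | Registration cancelled; no rule keeps the patient | Out |
| Dosed, never reassessed | In | In | Out |
| Dosed and reassessed, measurable disease | In | In | In |

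The row for undosed patients has no route into the primary analysis that the plan states clearly.

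**2. The plan's own figures.** Inputs from 13.2.2: n = 20, at least 6 responses, 15% versus 40%, exact binomial.

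- Power: P(X ≥ 6 | 20, 0.40) = 0.8744, against a stated figure of about 87%.
- Type I error: P(X ≥ 6 | 20, 0.15) = 0.0673, against a stated 0.07.
- Widest 90% exact interval, at 10/20: 30.2% to 69.8%, against a stated ±20 points.

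All three reproduce. They apply to whichever 20 patients are counted.

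**3. Effect on the response rate.** The documents give no number of undosed registrations, so k below is an assumption. Take 6 responders among 20 dosed patients and restore k cancelled registrations to the denominator, giving 6/(20 + k):

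- k = 0: 6/20 = 30.0%
- k = 1: 6/21 = 28.6%
- k = 2: 6/22 = 27.3%
- k = 3: 6/23 = 26.1%

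The drop is 1.4 to 3.9 points. The responder count stays at 6, so the decision rule gives the same answer.

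**4. Effect on power if undosed patients count within the 20.** Then only 20 − k patients can respond, and power is P(X ≥ 6 | 20 − k, 0.40):

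| k | Power | Type I error |
|---|---|---|
| 0 | 0.874 | 0.067 |
| 1 | 0.837 | 0.054 |
| 2 | 0.791 | 0.042 |
| 3 | 0.736 | 0.032 |

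The plan must therefore say which 20 it means.

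**5. Effect on PFS and OS.** If every analysed patient has the same gap g in days, the median from registration equals the median from first dose plus g/30.4375 months. The medians below are assumptions, since the plan gives none.

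| Gap | Added months | Relative to a 3-month median | Relative to a 12-month median |
|---|---|---|---|
| 0 days | 0 | 0% | 0% |
| 5 days | 0.16 | +5% | +1% |
| 14 days | 0.46 | +15% | +4% |
| 28 days | 0.92 | +31% | +8% |

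The 5 days come from 4.3. The 28 days are an outer ceiling taken from the baseline window in section 10. That window runs from the baseline tests to the start of therapy, not from registration, so a 28-day gap would need every windowed test to fall on the day of registration. The 14 days are simply a value in between.

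**The case against.** The strongest reply is that cancellation is an instruction about registration records, not about the analysis. The plan never defines enrolled. No section says that a cancelled registration leaves the denominator, and 13.7 itself treats enrolled and dosed as potentially different. This stands as far as it goes: treated-only is the working result of reading 4.1, 4.3 and 13.7 together, not a statement in the plan. But 4.3 equates registration with entry on study, no section keeps or follows cancelled patients, and 13.5 excludes them whatever the registration record shows.

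Second, the effect is modest. A shift of 1.4 to 3.9 points is small beside a 90% interval of about ±20 points, the success rule is a count, and PFS and OS are secondary and descriptive. This also stands. Reporting a response rate in treated patients is a defensible choice in a single-arm study, provided that it is named as such.

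A reader might infer four stronger things that the documents do not support:

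- **That cancelled patients are replaced.** No section says so.
- **That DF/HCC sites have a guaranteed 28-day event-free period.** No limit is stated there, 28 days is only a loose ceiling, and same-day dosing gives no gap.
- **That no event of any kind can occur before the first dose.** This is strict only for death. Progression is merely unlikely to be recorded: no restaging is scheduled between baseline and first dose, and progression is a reason to leave therapy under 5.5. However, section 10 asks for imaging whenever progression is suspected, and 5.8 allows some treatment past progression.
- **That the stated power or significance level is wrong.** Both reproduce.

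**Conclusion.** The concern holds in this form. The intent-to-treat analysis promised in 13.7 is not delivered by the procedures in 4.1 and 4.3 and is contradicted by 13.5, so the primary set is in practice treated-only or narrower. PFS and OS measured from registration then contain a pre-dose interval free of deaths by construction.

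Its size rests on assumptions. With 1 to 3 undosed registrations, an observed 30.0% would be 28.6% to 26.1%, with the decision unchanged if 20 dosed patients are still accrued. The time-to-event inflation is negligible with prompt dosing. It could matter for short medians where dosing is delayed, chiefly at DF/HCC sites, where no interval is stated. The remedy should be made before analysis, because with about 20 patients in the powered group single exclusions are visible.

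**What to change.** Reconcile 13.5 and 13.7 in a single edit; changing 13.7 alone would leave 13.5 in contradiction.

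1. Define the primary set as all registered patients, including those whose registration was cancelled because no dose was given. Count these, and dosed patients without reassessment, as non-responders. Report the number of cancelled registrations and the reasons.
2. State that the accrual goal of 20 refers to dosed patients, so that the stated 87% power is kept.
3. Label any analysis restricted to treated patients as all treated, and start its PFS and OS at cycle 1 day 1.
4. If PFS or OS is also reported from registration in the full registered set, provide for vital status of undosed patients, which 5.6 does not cover.

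Administrative cancellation in OnCore can stay as it is. The cost is a few sentences and a short list of cancelled registrations, plus survival contacts for those patients if item 4 is used. The downside is a response rate that may be slightly lower.

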4.2 Registration Process for DF/HCC Institutions

DF/HCC Standard Operating Procedure for Human Subject Research Titled *Subject Protocol Registration* (SOP #: REGIST-101) must be followed.

4.3 General Guidelines for Other Investigative Sites

Eligible participants will be entered on study centrally at the DF/HCC by the Project Manager. All sites should call the Project Manager at [contact] to verify study slot availabilities.

Following registration, participants should begin protocol therapy within 5 days. Issues that would cause treatment delays should be discussed with the Overall PI. If a participant does not receive protocol therapy following registration, the participant's registration on the study must be canceled. The Project Manager should be notified of cancellations as soon as possible.

4.4 Registration Process for Other Investigative Sites

To register a participant, the following documents should be completed by the research nurse or data manager and e-mailed to the DFCI Project Manager:

- Copy of required laboratory tests including: All screening evaluations.
- Signed informed consent document
- HIPAA authorization form (if separate from the informed consent document)
- Other appropriate forms (e.g., Eligibility Screening Worksheet, Registration form)

The research nurse or data manager at the participating site will then call [contact] or e-mail [contact] to verify eligibility. To complete the registration process, the Coordinator will follow DF/HCC Standard Operating Procedure for Human Subject Research Titled Subject Protocol Registration (SOP #: REGIST-101) and register the participant on the protocol. The coordinator will fax or e-mail the participant study number, and if applicable the dose treatment level, to the participating site. The coordinator will also call the research nurse or data manager at the participating site and verbally confirm registration

5. TREATMENT PLAN

5.1 Treatment Regimen

The rationale for selection of doses to be used in this trial is provided in Section 2.3 – Rationale.

Details on preparation and administration of pembrolizumab are provided in the Pharmacy Manual.

Pembrolizumab will be administered once every 3 weeks, with 21 consecutive days defined as a treatment cycle (unless the treatment cycle length is increased for adverse effect, as detailed in Section 6). Treatment will be administered on an outpatient basis. Reported adverse events and

potential risks are described in Section 7. No dose reductions are allowed. No investigational or commercial agents or therapies other than those described below may be administered with the intent to treat the participant's malignancy.

All participants will receive pembrolizumab at a fixed dose of 200 mg intravenously every 3 weeks for up to 35 cycles (approximately 2 years) or until disease progression, prohibitive toxicity, withdrawal of consent, or investigator discretion.

5.2 Pre-Treatment Criteria

5.2.1 Cycle 1, Day 1

In order to receive the first dose of study treatment, the participant must meet all of the eligibility criteria. All study therapy will occur in the outpatient setting.

5.2.2 Subsequent Cycles

Trial treatment should be administered on Day 1 of each cycle after all procedures/assessments have been completed as detailed in the study calendar (Section 10). Trial treatment may be administered up to 3 days before or after the scheduled Day 1 of each cycle due to administrative or logistical reasons.

A bone marrow biopsy at screening will only be required if patients have unexplained cytopenias of grade 2 or greater at baseline or if PET/CT is suggestive of bone marrow involvement.

As detailed in Section 6, pembrolizumab administration should be held for grade 4 hematologic events or grade 3 non-hematologic events, if the event is judged to be at least possibly related to study drug. In all cases, dose delay, treatment discontinuation, and toxicity management for immune-related adverse events should follow the guidelines in Section 6. In addition, treatment should be delayed if the subject's resting oxygen saturation is <94% while breathing ambient air. Criteria to resume treatment are also listed in Section 6.

5.3 Agent Administration

The general instructions for study drug preparations can be found in the MK-3475 Pharmacy Manual.

The drug will be provided as a solution for infusion, 100mg/vial. MK-3475 Solution for Infusion vials should be stored at refrigerated conditions (2 – 8 °C) and protected from light. Note: vials should be stored in the original box to ensure the drug product is protected from light. Parenteral drug products should be inspected visually for particulate matter and discoloration prior to administration. Discard the drug product vial if opaque or extraneous particulate matter other than proteinaceous particles is observed. In addition, the following precautions should be observed:

- Do not shake or freeze the vial(s).

- Do not administer the product as an intravenous (iv) push or bolus.
- Do not combine, dilute or administer it as an infusion with other medicinal products.

5.3.1 Dose calculation

The dose on this trial is a flat dose of 200 mg for all patients regardless of weight or body surface area.

5.3.2 Drug Administration

Pembrolizumab infusions will be administered as a 30 minute IV infusion, with a window of -5 and +10 minutes, using an infusion pump. A central catheter is not required for infusion; however if a subject has a central venous catheter in place, it is recommended that it be used for the infusion. No pre-hydration is necessary. The pharmacy manual contains specific instructions for the preparation of the pembrolizumab infusion fluid and administration of the infusion solution.

5.4 General Concomitant Medication and Supportive Care Guidelines

5.4.1 Concomitant Medications/Vaccinations (Allowed & Prohibited)

Medications or vaccinations specifically prohibited in the exclusion criteria are not allowed during the ongoing trial. If there is a clinical indication for one of these or other medications or vaccinations specifically prohibited during the trial, discontinuation from trial therapy or vaccination may be required. The investigator should discuss any questions regarding this with the Merck Clinical team. The final decision on any supportive therapy or vaccination rests with the investigator and/or the subject's primary physician.

The following concomitant treatments are prohibited during the treatment phase of this study:

- Anti-neoplastic systemic chemotherapy or biological therapy
- Immunotherapy not specified in this protocol
- Investigational agents other than pembrolizumab
- Radiation therapy except in selected cases, radiation to a localized area(s) of symptomatic disease may be allowed, after consultation with the study chair, and if the radiated lesions are not the target lesions for response assessment. In such cases, pembrolizumab treatment will be interrupted during the radiotherapy.
- Live vaccines within 30 days prior to starting treatment and while receiving study treatment.
- Immunosuppressive therapy.
- Systemic glucocorticoids for any purpose. The use of physiologic doses of corticosteroids may be approved after consultation with the overall Principal Investigator. NOTE: Systemic steroids can be given as premedication for blood products, treatment of adverse events, and/or contrast media for imaging procedures.
- Intravenous immune globulin is allowed at the discretion of the treating physician for replacement of immune globulin deficiencies.

Subjects who, in the assessment of the investigator, require the use of any of the aforementioned treatments for clinical management should be removed from the trial.

All treatments that the investigator considers necessary for a subject's welfare may be administered at the discretion of the investigator in keeping with the community standards of medical care. All concomitant medication will be recorded on the case report form (CRF) including all prescription, over-the-counter (OTC), herbal supplements, and IV medications and fluids. If changes occur during the trial period, documentation of drug dosage, frequency, route, and date may also be included on the CRF.

All concomitant medications received within 28 days before the first dose of trial treatment and 30 days after the last dose of trial treatment should be recorded. Concomitant medications administered after 30 days after the last dose of trial treatment should be recorded for SAEs and ECIs as defined in Section 7.2.

The exclusion criteria describe other medications which are prohibited in this trial.

There are no prohibited therapies during the post-treatment follow-up phase.

Nausea/vomiting: Nausea and vomiting should be treated aggressively, and consideration should be given in subsequent cycles to the administration of prophylactic antiemetic therapy per standard institutional practice. Subjects should be strongly encouraged to maintain liberal oral fluid intake.

Infection: Subjects with a documented infectious complication should receive oral or IV antibiotics or other anti-infective agents as considered appropriate by the treating investigator for a given infectious condition, according to standard institutional practice.

Cytopenias: growth factors and blood product transfusion support are allowed on this trial.

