11. MEASUREMENT OF EFFECT

11.1 Response Criteria

The primary objective of this study is overall response rate (ORR). Response and progression will be evaluated following the 2014 Lugano criteria for the primary endpoint and LyRIC for secondary endpoint. Patients will undergo tumor restaging, using the appropriate combination of imaging and bone marrow biopsies, after cycles 2 and 5 and 8 and then every 4 cycles thereafter until cycle 32. Radiographic restaging will also be performed at the 60-day post-treatment follow-up visit and at pre-specified intervals thereafter (see Study Calendar, section 10). Imaging will consist of PET/CT scans until the patient has achieved a metabolic CR (defined as Deauville score 1-3) at which juncture transition to CT of the chest, abdomen and pelvis will be acceptable at the discretion of the treating physician. Response assessment will follow standard criteria (Lugano criteria) for lymphoma. Bone marrow biopsy will be required within 30 days of radiology testing to confirm CR for patients with marrow involvement at baseline. A repeat bone marrow biopsy is not necessary to confirm CR if there was no marrow involvement at baseline.

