11.2 Evaluation of Best Overall Response

The best overall response is the best response recorded from the start of the treatment until disease progression/recurrence (taking as reference for progressive disease the smallest measurements recorded since the treatment started). The patient's best response assignment will depend on the achievement of both measurement and confirmation criteria.

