APPENDIX B

LUGANO AND LYRIC RESPONSE CRITERIA (31, 32)

Criteria	CR	PR	PD
Lugano	PET-CT, score 1, 2, or 3* with or without a residual mass on 5PS [†] OR on CT, target nodes/nodal masses must regress to ≤ 1.5 cm in LDi	PET-CT score 4 or 5 with reduced uptake compared with baseline and residual mass(es) of any size. OR On CT $\geq 50\%$ decrease in SPD of up to 6 target measurable nodes and extranodal sites	
PET-CT score 4 or 5 with an increase in intensity of uptake from baseline and/or new FDG-avid foci consistent with lymphoma at interim or end-of-treatment assessment. OR On CT, an individual node/lesion must be abnormal with: LDi > 1.5 cm and increase by $\geq 50\%$ from PPD nadir and an increase in LDi or SDi from nadir 0.5 cm for lesions ≤ 2 cm 1.0 cm for lesions > 2 cm
 
In the setting of splenomegaly, the splenic length must increase by $> 50\%$ of the extent of its prior increase beyond baseline (eg, a 15-cm spleen must increase to > 16 cm). If no prior splenomegaly, must increase by ≥ 2 cm from baseline. New or recurrent splenomegaly
 
New or clear progression of preexisting nonmeasured lesions
 
Regrowth of previously resolved lesions
 
A new node > 1.5 cm in any axis or a new extranodal site > 1.0 cm in any axis; if < 1.0 cm in any axis, its presence must be unequivocal and must be attributable to lymphoma
 
Assessable disease of any size unequivocally attributable to lymphoma
 
AND/OR new or recurrent involvement of the bone marrow
 
As with Lugano with the following exceptions:

LYRIC	Same as Lugano	Same as Lugano	
IR
 
IR(1): $\geq 50\%$ increase in SPD in first 12 weeks
 
IR(2): $< 50\%$ increase in SPD with
 
a. New lesion(s), or
 
b. $\geq 50\%$ increase in PPD of a lesion or set of lesions at any time during treatment
 
IR(3): Increase in FDG uptake without a concomitant increase in lesion size meeting criteria for PD

- IR, immune response; LDi, longest diameter; PPD, product of the perpendicular diameters; SDi, short diameter; 5PS, 5-point scale.
- d* A score of 3 in many patients indicates a good prognosis with standard treatment, especially if at the time of an interim scan. However, in trials involving PET where de-escalation is investigated, it may be preferable to consider a score of 3 as inadequate response (to avoid undertreatment).

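### On-study radiotherapy to non-target lesions can produce a PET response credited to pembrolizumab, because best overall response has no cut-off at radiation

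*Combined protocol and SAP*

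**What the plan says.** Section 5.4.1 lists radiotherapy among the prohibited concomitant treatments but makes an exception: "radiation to a localized area(s) of symptomatic disease may be allowed, after consultation with the study chair", provided the site is not a target lesion ("if the radiated lesions are not the target lesions for response assessment"). The study drug is paused, not ended: "In such cases, pembrolizumab treatment will be interrupted during the radiotherapy". The same section closes by saying that subjects who require "any of the aforementioned treatments for clinical management should be removed from the trial".

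Section 11.1 sets the imaging method: "Imaging will consist of PET/CT scans until the patient has achieved a metabolic CR". Appendix B then gives two routes to response. The CT route refers to target lesions. The PET route uses the 5-point score for CR, and a score of 4–5 with uptake below baseline for PR; neither PET definition mentions target lesions. Progression can also come from disease outside the target set: "New or clear progression of preexisting nonmeasured lesions".

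Section 11.2 defines the window: "The best overall response is the best response recorded from the start of the treatment until disease progression/recurrence". Sections 11.2.1 and 11.2.2 define duration of response, duration of CR and PFS without mentioning radiation, and Section 13 has no rule for irradiated patients.

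**The concern.** The safeguard and the response criteria do not match. Keeping radiation off target lesions protects a sum of diameters measured on those lesions. It does not protect a PET score that can be set by any avid site. A post-radiation scan stays inside the best-response window, so a local radiation effect can be recorded as a drug effect.

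The trial is open-label and single-arm, so there is no comparator in which the same thing would happen. The investigator and study chair decide who is irradiated, knowing how each patient is doing. The likely direction is predominantly favourable to the drug. The endpoints most exposed are the CR rate and duration of CR. ORR, duration of response and PFS are exposed in narrower circumstances.

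**Working it through.** **Which endpoints can move**

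| Situation | PET reading after radiation | Endpoints affected |
|---|---|---|
| Metabolic PR; the only site still at score 4 is non-target and is irradiated | Score 1–3, so CR | CR rate, duration of CR; ORR unchanged, since PR already counts |
| No response yet; one non-target site alone prevents PR or CR | PR or CR | ORR, CR rate, duration of response |
| A non-measured lesion is growing and is irradiated before a scan shows PD | PD may never be recorded | PFS, duration of response; the best-response window also stays open |

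By the CT route, radiation to a non-target lesion cannot itself produce a PR, because that PR rests on the target sum. The 5.4.1 condition works there.

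**Does another provision supply the missing cut-off?**

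- Study calendar footnote d stops imaging at new anti-cancer therapy, but only for patients who have already discontinued without progression.
- Footnote h calls for a scan whenever progression is suspected. This narrows the third row. It does not limit what a later scan may add to best response.
- Section 11.2.3 gives radiographic reading to an imaging core or equivalent. A core reader can score a post-radiation scan correctly and still record a CR, because the criteria allow it.
- The removal sentence in 5.4.1 conflicts with a drug that is only interrupted. Even if removal applied, 11.2 would set no response cut-off.

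**The plan's own figures**

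Inputs from Section 13.2.2: n = 20, success if at least 6 respond, null 15%, alternative 40%.

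- P(Bin(20, 0.15) ≥ 6) = 0.0673; the plan states 0.07.
- P(Bin(20, 0.40) ≥ 6) = 0.874; the plan states about 87%.

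Both reproduce.

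**Scale of one misattributed responder (assumed, not observed)**

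- One of the 20 patients is certain to be counted as a responder and the other 19 respond at 15%: P(Bin(19, 0.15) ≥ 5) = 0.144.
- One true non-responder is counted as a responder, so 5 true responses among 20 suffice: P(Bin(20, 0.15) ≥ 5) = 0.170.

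The risk rises from 0.067 to 0.144–0.170, a factor of 0.144/0.067 = 2.1 to 0.170/0.067 = 2.5.

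Alternatively, suppose a share f of true non-responders is reclassified. The apparent rate is then 0.15 + 0.85f:

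| f | Apparent rate | P(≥ 6 of 20) |
|---|---|---|
| 0.02 | 0.167 | 0.103 |
| 0.05 | 0.1925 | 0.172 |
| 0.10 | 0.235 | 0.323 |

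**One patient as a share of a rate**

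- 1/20 = 5 percentage points.
- At the expected lymphoma accrual of 24–30 (Section 13.2.1): 1/24 = 4.2 and 1/30 = 3.3 points.
- In the six-patient histiocytic/dendritic group: 1/6 = 16.7 points.

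**The case against.** The strongest reply is that this is rare and already hedged. Radiation is confined to selected cases after consultation with the study chair, and a symptomatic growing lesion should be scanned under footnote h. If that scan shows PD, best response closes and the PFS event is counted; later radiation cannot undo either. This stands. The hidden-progression case needs a lesion that is irradiated without such a scan, or while still short of PD.

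Appendix B also does not say in so many words that PET scoring covers all disease, and 5.4.1 does not define target lesions. The reading here is an inference: the PET definitions carry no target restriction, and non-measured lesions can define PD. It is the natural reading of the text, but an inference.

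A reader might go further and infer that radiation inflates ORR, or that the bias always favours the drug. The documents do not support either. Conversion of PR to CR leaves ORR where it was. Interrupting pembrolizumab during radiotherapy could work against response. The false-positive figures assume a misattributed responder, and nothing in the documents shows that one will occur.

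Finally, censoring duration of response and PFS at radiation is open to challenge. Patients irradiated for symptoms may be doing worse than others, so censoring them may be informative and lengthen both endpoints. This also stands, and it is why the remedy does not rest on censoring alone.

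**Conclusion.** The gap is real. As written, the plan can credit a CR produced by radiation, and occasionally a PR, to pembrolizumab. The main exposure is the CR rate and duration of CR. ORR, duration of response and PFS are exposed only where the irradiated site alone blocked a response or would have defined progression.

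The size is unknown because no frequency of on-study radiation is given. The 0.14–0.17 false-positive range is a yardstick that assumes one misattributed responder at the 6-of-20 bar; it is not an estimate of actual inflation. The conclusion rests on reading Appendix B's PET definitions as not confined to target lesions. The change is worth making because it is cheap and the trial is small.

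**What to change.** 1. **Section 11.2.** State that, for a patient irradiated on study for the study disease, assessments after the first radiation cannot improve best overall response under Lugano or LyRIC, whether or not the lesion was a target. Progression seen later still counts.
2. **Sections 11.2.1 and 11.2.2.** Report duration of response and PFS both ways: with radiation for symptomatic disease counted as an event, and with censoring at the last evaluation before radiation. Note that the censoring may be informative.
3. **CRF.** Confirm that it captures radiation date and site. Section 5.4.1 requires recording of concomitant medication and does not name radiotherapy, so a field may have to be added.
4. **Section 5.4.1.** Reconcile the radiation exception with the sentence on removing subjects who need a listed treatment.

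The clinical permission to irradiate is untouched, and sample size and decision rule do not change. The cost is a few sentences of endpoint definition and possibly one CRF field. The downside is that true late responses in irradiated patients are not counted, so ORR or the CR rate may be slightly lower.
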